1. LAY SUMMARY

Post-traumatic stress disorder (PTSD) is a mental health condition affecting an important minority of people exposed to traumatic life experiences such as life-threatening violence or sexual threat. The latest evidence shows up to 17% of UK ex-military service personnel who have recently deployed in combat roles may have PTSD. Undiagnosed or untreated, PTSD increases hospitalisation, unemployment, places a strain on family relationships and poverty.

We initially proposed to conduct a small trial in Northern Ireland to see the feasibility of providing 60 veterans diagnosed with PTSD with a novel treatment approach. However, due to recruitment difficulties which resulted from the Covid-19 pandemic, and with approval from Forces in Mind Trust (and ethical approval from King's College London and Queen's University Belfast), the project team began to recruit veterans from across the UK to the PETT study on 01.10.2020. If this trial is successful, then a future larger trial across the UK will compare the new treatment with **Trauma Focused Cognitive Behavioural Therapy (TF-CBT)** – A Gold Standard treatment with proven effectiveness.

The novel treatment is Reconsolidation of Traumatic Memories (RTM) – A therapy developed in the USA. RTM is based on Neurolinguistic Programming (NLP) which is an approach that aims to understand language patterns and intentionally change them to enable someone to think and/or feel differently about something that had previously distressed them. It is widely used by UK veteran charities even though the treatment is untested in relation to its effectiveness in addressing the symptoms of PTSD. Studies of RTM with US veterans report low dropout rates with most participants PTSD symptom free at six-week follow-up. Within these studies, the majority of veterans who did not respond to RTM had active substance abuse problems. RTM appears quick to administer and demonstrates positive results and is well tolerated. However, there is a lack of data showing whether it may have the potential to also cause harm, deter future help-seeking, or be more costly than other, well established, treatments for PTSD.

Our charity partner, Inspire, will provide these treatments to study participants. People taking part will be randomly allocated to either TF-CBT or RTM therapy. Inspire have considerable experience and expertise in delivering psychological therapies to veterans with PTSD who served in Northern Ireland. Inspire therapists will be trained to deliver both interventions and will be supervised by experts in these therapies.

Within 28 months, we will:

- Train Inspire's therapists in TF-CBT and RTM treatments;
- Recruit and allocate 60 participants randomly to either treatment;
- Calculate how many veterans remain in the trial/treatment and understand reasons for drop-out;
- Collect questionnaire data at 6, 12, 20 and 52 weeks post randomisation;
- Determine the acceptability of the treatments and the research trial for participants and any barriers to participation.

Beneficiaries include:

- Inspire's therapists Upskilled through training in the two treatments;
- Veterans and their families Potential reduction in PTSD symptoms and identification of veteran and PTSD profiles for whom this treatment appears to work best/not work so effectively.
- Veterans, their families, Research Partners and wider mental health sector Knowing whether a larger trial of RTM is justified and, if so, how a larger trial might best be undertaken;

 Research Partners - Upskilled by research involvement. Increased visibility of services within the veteran community and beyond.

2. BACKGROUND

The original PETT study was to be conducted in partnership with recruitment and treatment delivery partner, Inspire, who are based in Northern Ireland (NI)). However, as a consequence of the Covid-19 pandemic that developed throughout 2020 we soon realised that due to a huge reduction in referrals to NI charity organizations and veteran support services of veterans with suspected PTSD, unless we broadened our recruitment strategy to the whole of the UK we would be unable to recruit sufficient numbers of participants within our timescales. The opportunity to expand beyond NI to help overcome participant referral and conversion rate challenges was discussed with and received approval from FiMT (and later, ethical approval from KCL and QUB) in September 2020. The PETT study has since begun recruiting veterans from across the UK (from 1st October 2020). We continue to recruit participants from NI and our analysis will be able to support our original methodological rationale as well as the additional data from the rest of the UK.

For background detail and in our original proposal, Post-Traumatic Stress Disorder (PTSD) presents a significant burden to the veteran community negatively impacting function, physical health and family relationships (1-3). In Northern Ireland (NI) this is complicated further because of *The Troubles* which means veterans who served in Northern Ireland live in the community alongside the former perceived enemy, ex-combatants and may well continue to fear for their security which may deter help-seeking(4). The PTSD prevalence in NI's general population is 5% in any previous 12 months. This is comparable with 4.4% in the UK for the past month (5-7). It has an estimated annual economic cost of £172M (5). Rates of PTSD in some UK veterans, particularly those whose last deployment was in a combat role, is around 17% (8). In NI, veteran PTSD prevalence data is not yet available but it is expected to be high because of the context of *The Troubles* (9, 10).

NI veterans with mental health issues experience barriers to accessing NHS psychological services including reluctance to both register with a GP, and if they do, a reluctance to disclose their veteran status (9, 10). Additionally there are high levels of social exclusion, low confidence in NHS services and stigma (11, 12). Recent reports concluded veterans should be able to self-refer, access services through charities and encounter health professionals who are themselves veterans (11). Charities report experiencing increased referrals every year (13). Many such UK charities are too small to work with and we sought a charity partner with appropriate levels of clinical, information and financial governance to support a robust research evaluation. This led us to Inspire in NI. In NI providing bespoke healthcare access for veterans is challenging due to the lack of dedicated veteran NHS services (14) and waiting list treatment targets of 52 weeks, compared to 18 weeks elsewhere in the UK (4). This is unfortunate as evidence suggests that over time, untreated PTSD symptoms are unlikely to resolve although the associated psychological distress and psychosocial deficit increases (1). Recommended treatments for PTSD are TF-CBT and Eye Movement Desensitisation and Reprocessing (EMDR) (15) which ordinarily involves between 8 and 20 therapy sessions (16). NICE, however, recommends EMDR for PTSD only where the trauma is NOT combat-related (17). Furthermore, a review by Kar et al (2011) (18) reported up to 50% non-response rates to TF-CBT and high attrition is reported (19) and response rates to these treatments in veterans can be marginal (20). A need for new and/or improved interventions, trauma and non-trauma focused, for PTSD in veterans has been identified (20, 21). Neurolinguistic programming (NLP) is a treatment of choice for many charities delivering mental health support (22-27) because it therapeutically avoids the trauma focus (28), is quick to deliver and is without statutory regulation. The experimental RTM Protocol intervention is an

intervention based on Neurolinguistic Programming (NLP). NLP is a psychotherapeutic approach that seeks to understand and change a person's thinking and behaviour and proposes that the way we understand our world depends on which of our senses, vision, hearing, taste or touch are more dominant (29). A person's dominant sense is communicated mainly by what we say and how our eyes move. For example, a visual person may say '*I see what you mean*' whereas a person with a dominant hearing sense will say '*I hear what you say*'. The central hypothesis of NLP is that communication will be more effective, persuasive and therapeutic if it is tailored to match the preferred senses of the target person. There are a number of charities delivering NLP therapy to military veterans (22-27) in the absence of evidence for its effects and impacts (29).

Devolved Governments, the NHS veteran service and key charities are concerned about use of NLPbased therapy with veterans (30). In four small US veteran studies, the NLP-based Reconsolidation of Traumatic Memories (RTM) protocol offered possible treatment advantages (28, 31-33). Therapy completion was 88%, symptoms abated in three sessions, considerably fewer than up to 12-18 for complex PTSD. It was acceptable to and well tolerated by veterans, practitioner training was rapid and manualised and third sector delivery offered wider access therefore, adding to the choice of the armoury of effective therapies. On the other hand, because the US studies were under-powered there are many unknowns and it remains possible that, in some instances, RTM may potentially elicit a deterioration in clinical symptoms, deter future help-seeking, or be complex and costly to deliver at scale. Additionally, there are no pilot or feasibility data which currently exists (28, 31-33) to distinguish the impacts of RTM in veterans with complex PTSD as proposed by the International Classification of Diseases 11th revision (34).

Academic psychology has criticised NLP-based interventions for lack of a theoretically driven framework and little robust evidence of efficacy derived from gold standard RCT trials (35, 36). Despite anecdote of positive NLP effects from real world practice with veterans (22-26), a systematic review and Freedom of Information request (29) found no robust gold standard evidence of efficacy alongside some modest NHS expenditure on poorly-defined NLP activity. This absence of evidence is not absence of effectiveness. We are unclear whether the RTM protocol is effective, above all else does no harm and is value for money. It is essential, therefore, for the international veteran community to understand whether this treatment intervention for PTSD holds the potential for healing (equivalent to existing evidence-based treatments) that it promises by working towards a scientifically rigorous approach to its evaluation.

The current study has been designed to maximise the availability of both TF-CBT and RTM therapies to those most in need of treatment. The additional training that will be provided to Inspire therapists will increase the pool of therapists with the pre-requisite knowledge and skills to deliver TF-CBT in multiple and remote Inspire treatment centres outside of Belfast. Whether RTM eventually proves to be an effective treatment for PTSD or not, our study will leave a legacy of improved mental health trauma service provision across NI.

3. METHODS AND STUDY DESIGN

3.1 Aims and Objectives

To undertake a pilot RCT as a precursor to a fully-powered non-inferiority RCT. The pilot will determine rates of participant recruitment, randomisation, treatment and research attrition and completeness of outcome data prior to establishing whether a fully-powered non-inferiority RCT is feasible.

The external pilot RCT will:

1: Determine the rate of trial recruitment, retention in treatment and research, understand reason for drop out and determine completeness of outcome data assessed against progression criteria to determine if a fully powered trial is deliverable;

2: Undertake exploratory analyses of the outcome data to support a power calculation for a fully powered non-inferiority trial;

3: Understand the safety risks;

4: Establish an expanded mental healthcare capacity across Northern Ireland to enable both interventions to be delivered close to the veteran's home.

3.2 Research questions

- a. Can Inspire therapists deliver both interventions according to their respective protocols?
- b. Will statutory and charity sectors refer to an experimental NLP-based therapy and by which referral pathway?
- c. What is the rate of presentation of veterans with diagnosed PTSD, comorbidity and Complex PTSD to Inspire in Northern Ireland (NI)?
- d. What is the level of complete and missing data and on which outcomes?
- e. Are the progression criteria met, specified as recruitment of 60 participants in 14 months; in each arm ≥70% of participants complete treatment; retention of ≥36 participants at 20 week follow-up?
- f. How does the safety protocol (see appendix 1) detect and limit the consequences of adverse events and what are the clinical governance implications of this?
- g. What is the per-participant cost of delivering RTM (including managing any adverse or serious adverse events)?

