3.6 Sample Size

The proposed external pilot sample size takes into account published recommendations for pilot trials (42, 43) which propose a method for determining an external pilot RCT sample size in order to minimise the sample size for the main RCT. This sample size will support the calculation of confidence intervals around the proportion of eligible participants who agree to take part in the research, and the attrition rates from both the treatments and the research. Our proposed sample size is 60, 30 in each arm. Initially, we had a 1:1 randomisation ratio. However, with 50% of our target randomisation figures achieved due to therapist attrition in the TF-CBT delivery arm we sought statistical advice and decided to change the randomisation ratio to 2:1 in favour of the experimental RTM. This would allow us to continue to recruit at the level required to fulfil our recruitment targets specified by our funder.

Treatment seeking in the veteran population is low (44, 45) and response rates to PTSD research invitations are poorly reported (46, 47). For example, Ulmer et al (2011) (48) screened 91 veterans with PTSD to recruit 22 participants to their pilot RCT. In a review of 7 randomised trials comparing TF-CBT with Eye Movement Desensitisation and Reprocessing, research and treatment attrition ranged from 8 - 58% with a mean of 29% (49). Taking these data into account, we propose to screen 180 people for eligibility, randomise 60 participants and expect an attrition of 30% and 50% (or lower) from the intervention and comparison respectively resulting in \geq 36 participants with data at 20 weeks follow up. A screening sample of 180 would be sufficient to obtain a 95% confidence interval for a

proportion of $\pm 8\%$ or narrower, and a sample of 60 for a 95% confidence interval of $\pm 13\%$ or narrower, both with 99.9% probability calculated using SAS POWER (50)

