Appendix 4. Progression criteria to a full non-inferiority RCT

Project	Measure of Success	Nature and number of	Timescale
Outcome 1:	In 14 months we identify 180 eligible	180 study participants	Months 5-18
Known rate of	narticinants		WOII(II3 J-10
trial			
recruitment,	Consenting and randomised	60 study participants	Months 5-18
retention in	participants $n = 60$		
treatment and	Treatment drop out:	>36 study participants	Months 5-21
research and	RTM protocol Intervention drop out ≤		
completeness	30%		
of outcome	TF-CBT intervention drop out ≤ 50%		
data assessed	Research attrition: Research follow up	36 study participants	At end of project
against our	retention 36 participants at 20 weeks		
green traffic			
light			
Outcome 2:	Baseline data set is complete for 90%	54 study participants	Months 5-18
Exploratory	of participants	54 study participants	WOIIIIIS 5-18
analyses of the	12 week follow up data set is complete	42 study participants	Months 8-21
outcome data	for 70% of study participants		
to support a	20 week data set is complete for 50%	30 study participants	At end of project
nower	of participants		
calculation for			
a fully powered			
non-inferiority			
trial.			
Outcome 3:	A trial adverse and serious adverse	All 60 trial participants	Month 2
Known safety	event definition and safety protocol is		
risks and	developed which identifies all		
amenorations	refers according to Inspire and		
ОГКПИТНЕГАРУ	research project-specific statutory care		
	pathways: contains adverse events (e.g.		
	relapse, hospital admission, suicide		
	and attempted suicide) across the 20		
	week follow-up period and		
	documented clinical actions taken to		
	mitigate participant risk		
	All adverse and serious adverse events	All 60 trial participants	Month 5-23
	and ameliorations recorded and every		
	event discussed at the bi-weekly		
	research team meeting.		
	A log of every adverse, serious adverse	All 60 trial participants	At end of project
	event and clinical and research team		
1	actions in response		

Outcome 4:	A minimum of 5 Inspire therapists will	The beneficiaries of an	Month 4
Establishment	complete the 20 hour masterclass and	expanded professional	
of expanded	be assessed as proficient in delivering	mental health capacity	
mental health	protocoled TF-CBT	across Northern Ireland	
care capacity	-	would be extensive.	
across	A minimum of 5 different Inspire		Month 4
Northern	therapists will complete the 70 hr RTM	Hitherto, TF-CBT has only	

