Ireland to	training and be assessed as proficient	been available to veteran	
enable both	in delivering the RTM protocol	members of the Armed	
interventions	Inspire therapists attend two – four	Forces aftercare service in	Month 21
to be delivered	weekly clinical supervision sessions	Belfast which for the	
within 20 miles		majority of veterans was	
of the		too far to travel weekly for	
veteran's		8-12 weeks.	
home.	≥50% of randomised participants to		At end of project
	the TF-CBT arm remain in treatment		
	when delivered closer to home		

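### The treatment-completion progression criterion for TF-CBT is stated two ways: at least 70% completing in section 3.2(e), but drop-out of up to 50% in Appendix 4

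*Protocol*

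**What the plan says.** Protocol section 3.2, question (e), asks whether the progression criteria are met and spells them out. After recruitment of 60 in 14 months it lists: "in each arm ≥70% of participants complete treatment; retention of ≥36 participants at 20 week follow-up". The 70% applies to both arms.

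Section 4.1.1, on progression to the full trial, contains only a pointer to Appendix 4, which is headed "Appendix 4. Progression criteria to a full non-inferiority RCT". Under Outcome 1, labelled as the green traffic light, the treatment drop-out row has two limits. For RTM it reads "RTM protocol Intervention drop out ≤" 30%. For TF-CBT it reads "TF-CBT intervention drop out ≤ 50"%. Outcome 4 repeats the TF-CBT limit from the other side: "≥50% of randomised participants to" the TF-CBT arm are to remain in treatment.

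Section 3.6 uses the same pair of percentages for planning. The team "expect an attrition of 30% and 50% (or lower) from the intervention and comparison respectively", and derives from this at least 36 participants with data at 20 weeks.

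**The concern.** Both section 3.2(e) and Appendix 4 present themselves as the progression criteria. For RTM they are the same rule, since 70% completion is 30% drop-out. For TF-CBT one requires at least 70% completion and the other at least 50%. A TF-CBT completion rate from 50% up to just under 70% is therefore a pass in one place and a fail in the other.

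Assessing retention against progression criteria is part of the pilot's first objective (section 3.1). If the conflict is still there when completion data are seen, the team can no longer show that its choice of threshold was independent of the result. Section 4.1 brings that moment forward: the traffic-light criteria are to be used once half the target sample has completed the intervention and 12-week follow-up.

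**Working it through.** **Inputs**

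- Total sample 60, planned as 30 per arm (section 3.6).
- Allocation changed from 1:1 to 2:1 in favour of RTM at 50% of target (section 3.6). The resulting arm sizes are not stated. Assuming 30 randomised at 1:1 and 30 at 2:1, RTM has 15 + 20 = 35 and TF-CBT has 15 + 10 = 25.
- Completion thresholds for TF-CBT: 70% (section 3.2(e)) and 50% (Appendix 4).
- Completion is read as the complement of treatment drop-out.

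**Step 1. Reproduce the plan's own figure of 36.**

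- 30% and 50% attrition, 30 per arm: 30 × 0.70 + 30 × 0.50 = 21 + 15 = 36. This matches exactly.
- Same rates with 35 and 25: 24.5 + 12.5 = 37, still consistent with at least 36.
- 70% retained in both arms: 60 × 0.70 = 42. This does not reproduce 36.

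The 36 thus goes with the 30%/50% pair, and section 3.2(e) is the odd one out.

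**Step 2. Completers needed in the TF-CBT arm.** The minimum is the threshold times n, rounded up.

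- n = 30: Appendix 4 needs 30 × 0.50 = 15, and 3.2(e) needs 30 × 0.70 = 21. Results of 15 to 20 completers (50% to 67%) are in conflict.
- n = 25: Appendix 4 needs 12.5, so 13, and 3.2(e) needs 17.5, so 18. Results of 13 to 17 completers (52% to 68%) are in conflict.

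**Step 3. Probability that the TF-CBT criterion is met.** With X ~ Binomial(n, p), this is P(X ≥ k), where k is the minimum from step 2. The true completion rate p is an assumption and is varied. The two rules disagree with a probability equal to the difference between the two columns.

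| n | true completion p | Appendix 4 | section 3.2(e) | rules disagree |
|---|---|---|---|---|
| 30 | 0.50 | 0.572 | 0.021 | 0.551 |
| 30 | 0.60 | 0.903 | 0.176 | 0.727 |
| 30 | 0.70 | 0.994 | 0.589 | 0.405 |
| 30 | 0.80 | 1.000 | 0.939 | 0.061 |
| 25 | 0.50 | 0.500 | 0.022 | 0.478 |
| 25 | 0.60 | 0.846 | 0.154 | 0.693 |
| 25 | 0.70 | 0.983 | 0.512 | 0.471 |
| 25 | 0.80 | 1.000 | 0.891 | 0.109 |

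**Step 4. The early look in section 4.1.** If the half of the sample used there contains about 15 TF-CBT participants (an assumption: the 1:1 half), the minima are 8 (from 7.5) and 11 (from 10.5). Results of 8 to 10 completers are in conflict. At p = 0.60 the criterion is met with probability of about 0.79 under Appendix 4 and 0.22 under 3.2(e).

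**The case against.** The best defence is that the intended rule can be worked out. Section 4.1.1 refers only to Appendix 4, Outcomes 1 and 4 there both use 50%, section 3.6 plans on 50%, and 36 follows from it. On this view 3.2(e) is a drafting slip. That stands as an argument about which text to correct. It does not remove the conflict, because 3.2(e) also says it specifies the criteria and no sentence gives Appendix 4 precedence. Nor can the two be read as tiers: Appendix 4 labels its own thresholds green, and no amber band is defined.

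The size also depends on the assumed completion rate. A true rate of 60% lies near the peak of disagreement; at 80% the rules differ with probability of only 0.06 (n = 30) or 0.11 (n = 25). That stands too, and it is why a range is shown.

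Four stronger readings are tempting, and the protocol does not support them:

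- A reader might infer that 70% is the right threshold, because 3.2(e) says so and section 3.6 cites mean attrition of 29%. That mean comes with a range of 8% to 58% and mixes research and treatment attrition, and the team settled on 50% for TF-CBT with those data in view.
- A reader might infer that the trial plans to fail 3.2(e). Section 3.6 gives 50% as a ceiling by adding that it may be lower, and ties it to 20-week data. Section 3.12.2 counts staying in treatment separately from staying in the research.
- A reader might call this the trial's main decision rule. It is one criterion beside recruitment, 20-week retention, data completeness, safety recording and therapist capacity.
- A reader might fear a false claim of non-inferiority through a weakened comparator. This pilot makes no non-inferiority claim; that question belongs to the later trial.

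**Conclusion.** The contradiction is real, is confined to the TF-CBT arm, and should be removed before the criterion is applied. The results in conflict are 15 to 20 completers out of 30, or 13 to 17 out of 25. For true completion between 50% and 70% the two rules disagree with probability 0.41 to 0.73 across the tabulated rates at n = 30, and 0.47 to 0.69 at n = 25. If completion were as low as the 50% planning ceiling, Appendix 4 would be met with probability 0.57 and 3.2(e) with probability 0.02 (n = 30).

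These probabilities concern the TF-CBT completion criterion alone, not the whole traffic light. They rest on reading completion as the complement of drop-out, on independent participants with a common completion rate, and, for n = 25, on an inferred split. The contradiction itself needs none of these beyond the first.

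**What to change.** State one TF-CBT threshold throughout the protocol, and date the change before completion data are used for the progression decision, including the early use described in section 4.1.

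The simplest correction is to rewrite section 3.2(e) to match Appendix 4: RTM drop-out up to 30%, TF-CBT drop-out up to 50%. Section 3.6, both Appendix 4 rows and the target of 36 then stand as they are. The cost is wording in one place.

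If the sponsor prefers 70% completion in both arms, both Appendix 4 rows (Outcome 1 and Outcome 4) must change. The 50% planning figure in section 3.6 and the 36 derived from it must then be revisited wherever they appear, since 70% in both arms corresponds to 42 of 60. This is still a matter of wording, but in more places. Neither route needs new data.
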